#### Explanation of risks in relation to anticipated benefits:

A documented and effective speech intervention program for individuals with DS may result in improved intelligibility and communication effectiveness, and guide efficacy in the field of speech language pathology. As stated above, the risks are minimal and prevention methods are in place. We do not anticipate any of the risks listed above to cause significant harm to participants. The anticipated benefits, on the other hand, are significant in that they assess the efficacy and advancement of an intervention strategies specific to improving speech intelligibility in individuals with DS.

#### Provisions to identify and address problems

The VTLab staff has taken preventative measures to eliminate unanticipated problems or potential complications and is in a position to resolve problems should any issues arise. In the unlikely case that unanticipated problems or complications arise, we will meet any unexpected medical emergency of our participants with appropriate response. All unanticipated problems or complications will be promptly reported to the IRB.

Should VTLab staff note any evidence of neglect or physical, emotional, sexual, or other abuse while conducting testing, we will as mandatory reporters, promptly report observations to the appropriate agency (e.g. Child Protective Services, Disability Rights Wisconsin).

### Statistical Considerations

Analysis will entail using a multiple single-subject design (Byiers, 2012) where assessment of progress for each of the 10 male participants will be compared against himself. This is based on the expected variability in speech production across participants. Assessment measures will include: a) speech-language quantitative measures described below including phonetic transcription by a trained speech-language pathologist; b) acoustic measures; and c) perceptual measures for intelligibility score (percent correct) that the VTLab has been using and described in detail in Wild et al. (2018).

The VTLab Speech Production (IRB protocol 2016-1025) task includes the recording of words and sentences that participants produce, which are then analyzed acoustically using TF32 (Milenkovic, 2010) to measure the vowel formants; intelligibility is scored as percent correct (words, consonants, vowels) based on the transcription of lab staff and/or naïve listeners. For each participant, assessment will entail three pre-treatment baseline measures, and post-treatment measures at the completion of the 12-week treatment, and at one, and six months following completion of DS-DxTx. The initial assessment also will include standardized testing using the Hodson Assessment of Phonological Processes-3 to customize treatment plan, Peabody Picture Vocabulary Test, an oral motor exam, Intelligibility in Context Scale (ICS) questionnaire, parent questionnaires, and language samples to measure Mean Length of Utterance, and when sample is adequately length for intelligibility scoring.

Consultation with a statistician, available through Waisman Center core services, will be used.

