The proposed intervention study to implement on individuals with DS, as described in the following section, is based on the natural evolution of research in the Vocal Tract Development Laboratory (VTLab) – as summarized in the previous section –. It is rooted in VTLab research findings from anatomic (working manuscript), acoustic (Vorperian et al., 2022 & 2019; Vorperian and Kent, 2014; Kent and Vorperian, 2013) and perceptual studies (Kent et al., 2021; Wild et al., 2018) on individuals with DS that the VTLab has been studying since 2000 with funding support from NIH-NIDCD. This proposed diagnostic treatment study (DS-DxTx) utilizes a holistic intervention approach that accounts for the likely motoric, phonologic and hearing loss deficits in individuals with DS. The smaller midfacial skeleton in individuals with DS has been hypothesized to cause crowding in the oral and pharyngeal cavities resulting in the disruption of all functions performed in the mouth and throat specifically respiration, deglutition and speech. Thus, a number of drastic surgical/medical interventions, such as tongue reduction, mandibular extraction and palatal expansion are commonly performed by medical professionals to address obstructive sleep apnea and drooling. This study is expected to provide the data needed to assess treatment efficacy in improving speech intelligibility; also, to provide the preliminary data needed to clarify the extent to which craniofacial dysmorphologies affects reduced speech intelligibility. The preliminary data from this study is expected to inform future clinical trials that examine the role of oro-pharyngeal functions, as an intervention strategy during early childhood, in the development of the anterior facial skeleton (functional anatomy).

**Aim 1:** Determine the efficacy of a newly devised intensive speech diagnostic treatment plan (DS-DxTx) that combines two established treatment approaches on articulatory accuracy and motor control (Cycles and the Script programs that are documented to be efficacious with other speech disorders) while predominantly using the low vowels as described below in the Methods section.

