Speech intelligibility is hypothesized to improve as phonological errors decrease. Perceptual measures to assess treatment efficacy include: **(a)** the HAPP-3 score of Total Occurrence of Major Phonological Deviations (TOMPD score = Word/Syllable Structure Omission Sum (that includes omission and consonant clusters) + Consonant Category Deficiencies Sum); and **(b)** Percent Words & Multisyllabic words Correct (with tabulation of percent consonants correct and percent vowels correct).

**Aim 2**: Determine the extent to which craniofacial dysmorphology affects reduced speech intelligibility using a combination of perceptual and acoustic measures.

Accuracy in the perceptual identification of the low vowels (percent vowels correct) is hypothesized to remain unchanged if reduced accuracy is predominantly due to craniofacial dysmorphologies (underdeveloped/shorted midface skeleton). Perceptual measure will include percent accurate identification of the low vowels /a/ versus /æ/ (% vowels correct) pre- versus post-treatment. Acoustic measure will include the first two resonant/formant frequencies of the vocal tract (F1 & F2) with

comparisons of pre- versus post- treatment acoustic measures (as well as VTLab TD normative values and DS acoustic data). Increased difference of the second resonant frequency (F2) for the low vowels / $\alpha$ / versus / $\alpha$ /, related to the functional front/back movement of the tongue in the horizontal plane, combined with improved perceptual identification of the low vowels (percent vowels correct) will implicate the effectiveness of intensive treatment on low vowels using articulatory accuracy and motor control.

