# Research Design and Method

### Approach

Participants with DS who speak English as their primary language will be recruited in this DS-DxTx study. Ten male speakers with DS ages 7 to 16 years will be enrolled in this study based on Wild et al. (2018) findings that males are less intelligible than females and that speech intelligibility improves up to age 16 years. Difficulty recruiting participants is not anticipated given available resources that we have used to recruit participants for former VTLab studies (Waisman Center's clinical and translational core, Goodnight Hall, and social media posts).

Procedures for DS-DxTx will entail formal intervention by a certified Speech-Language Pathologist and one assistant where each participant will receive an average of three hours of therapy/week over a 12 week period (36 required contact hours/participant), and 30 minutes weekly home practice using an app or flashcards/worksheets for therapy practice. Treatment will be in a quiet clinic room (location may include the Waisman Center, a local library/school, or GiGi's playhouse) with ongoing assessment of progress following ASHA best practice guidelines (ASHA, website March 13, 2018). All members involved in treatment will have HIPAA and CITI certification and be familiar with neglect/abuse and safety/security guidelines of vulnerable populations. They will also follow the universal cleaning precautions for all treatment and assessment materials. To ensure effective intervention, age appropriate activities and materials will be used during treatment while taking into account individual needs and interests.

The DS-DxTx study is rooted in Wild et al. (2018) findings that low vowels /a/ as in 'hot' and /æ/as in 'hat' are less intelligible than the high vowels /i/ as in 'heat' and /u/ as in 'boot'. As described above, contrary to the common practice of targeting consonants in treatment, the proposed DS-DxTx will focus on low vowel accuracy. We expect that vowel accuracy will also impact accuracy of consonant production at the syllable level and help improve overall speech intelligibility despite the anatomic and/or motoric limitations present in individuals with DS. This DS-DxTx treatment combines two well established treatment approaches with documented treatment efficacy, the Cycles and the Script programs described below, and adapts both to using vowels, specifically the low vowels /a/ and /æ/.

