Each DS-DxTx session will include 40 minutes of the adapted Cycles program focusing on articulatory (phonological) training at the syllable/word level and 20 minutes of the adapted Script program for motor training at the sentence level. The adaptations are to ensure vowel-focused intervention to facilitate low vowel production stability with repeated practice. The Cycles phonological program is a treatment guidance for typically developing individuals with moderate to severe unintelligible speech (Hodson, 1992; Hodson, 2006; Hodson, 2011). The focus is on assessing and treating speech sound disorders in targeted patterns based on developmental phonology. The name 'Cycles' refers to periods where all phonological error patterns are facilitated in succession per target

phoneme (Hodson & Paden, 1991) with gradual increase in complexity per cycle. The program uses auditory bombardment (wearing personal amplification while hearing the target sounds), production drill and sound practice (i.e. repeating sounds, syllables, & words as practice) in facilitated context to yield accurate productions. The development phonological treatment is syllable units, consonant vowel (CV), VC, CVC or VCV, /s/ clusters and alveolars in words, then phrases. Currently, no efficacy data has been reported using the Cycles phonological treatment program with individuals with DS. However, individuals with DS often have moderate to severely unintelligible speech and a potential fluctuating history of otitis media (Hodson & Paden 1991). The Cycles design uses amplification and habituates accurate syllables through repeated practice which may assist with a fluctuating hearing loss and motor control planning (e.g., apraxia, dysarthria). Modifications to Cycles specific to this treatment plan is the vowel-focused intervention that establishes distinct contrasts of the low vowels  $/\alpha$  and  $/\alpha$  that may result from anatomic and/or motor limitations. Facilitating low vowel stability while still following the targeted cycles of phonological intervention repeated practice adheres to the Cycles program design. Reducing the variability and automatizing productions of anticipatory sounds at the syllable level may improve co-articulatory effects of consonant accuracy in words. Priority of  $/\alpha$  and  $/\alpha$  vowels will supersede other vowel productions within each cycle of the treatment program.

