### Participants: Identification and recruitment

The following steps/criteria will be used:

Participants will include ten male participants with DS between the ages of 7-16 years old who want to improve their speech intelligibility.

Inclusion criteria: Participant eligibility criteria for this protocol, will be assessed by phone eligibility script (uploaded document titled "Phone screening form") completed by parent/guardian to meet the following criteria:

- Males with a diagnosis of DS between the ages of 7 and 16 years, whose primary language is English, and who are interested in improving their speech intelligibility. All participants must consent/assent to participate.
- As this is a multiple single subject design study, services are available to all motivated participants who are willing to commit to the time/durations described in the diagnostic treatment.

During the phone interview the following information will be collected from participants:

 Date of birth, primary language is English, sex, date of birth (to confirm the subject's/participant's age and to ensure subjects/participants meet eligibility requirements), telephone, address, and/or e-mail address to contact the participant in case an appointment needs to be cancelled/rescheduled or the participant does not show up, cursory speech, language, orthodontia & hearing history, and medical conditions/health issues that may affect speech, language or hearing.

While consenting, all prospective participants will have the opportunity to 'agree' or 'not to agree' to the treatment plan.

Exclusion criteria: Individuals will be excluded if American English is not their primary language, they do not have Down syndrome, or are a female. Individuals who have a co-occurring diagnosis that affects communication abilities (e.g., diagnosed as deaf with cochlear implants, Autism, only use an AAC device to communicate) or a severe hearing loss which will limit their ability to participate in the treatment as described above will also be excluded. Individuals with a known mild or moderate hearing loss or current speech-language therapy services will not be excluded, but this information will be requested in the Parent Questionnaire as well as access to their current IEP.

Recruitment may occur from the following sources:

- Internet
- Newsletters
- Poster/ fliers

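### With each boy compared only with himself, modest changes or changes seen only at six months in the Aim 1 measures cannot be attributed to DS-DxTx, so the efficacy wording goes too far

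*Combined protocol and SAP*

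**What the plan says.** Statistical Considerations describes a multiple single-subject design in which "assessment of progress for each of the 10 male participants will be compared against himself". Each boy has three baseline measures, then measures at the end of the 12-week treatment and one and six months later. The Measures section limits the baseline phase to three sessions and does not give their spacing.

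Aim 1 (Specific Aims/Study Objectives) is to "Determine the efficacy of a newly devised intensive speech diagnostic treatment plan (DS-DxTx"). Its measures are TOMPD, taken from the HAPP-3, and percent words correct. Potential Benefits likewise says that the study can serve to establish efficacy.

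Three other statements bear on how a change would be read:

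- Approach sets the age range of 7 to 16 on the finding that "speech intelligibility improves up to age 16 years".
- The exclusion criteria say that boys with "current speech-language therapy services will not be excluded". The IEP, the phonological targets and a Parent Questionnaire are requested.
- The post-treatment visits repeat the word and sentence recordings, the language sample and the HAPP-3.

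The section How risks will be minimized gives an ethical reason for having no control. It also cites another study in which treated items changed more than untreated ones.

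**The concern.** A fall in TOMPD or a rise in percent words correct after treatment has up to four possible sources: DS-DxTx, growth, practice on repeated tasks and, for boys in therapy, that therapy. A single-subject design usually separates these with a staggered start, a stable or modelled baseline, or items left untreated. None of these appears anywhere in the document, and there is no concurrent control. The therapy information is requested, but no analysis uses it.

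The one outside reference is in Aim 2, where acoustic values are compared with laboratory data ("as well as VTLab TD normative values and DS acoustic data"). It covers formant frequencies, not the Aim 1 measures.

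If the plan is followed as written, an uncontrolled change could be reported as efficacy of a treatment for which the protocol says no evidence-based guidance exists.

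**Working it through.** **The plan's own figures.** Contact time reproduces: 3 hours a week x 12 weeks = 36 hours. The sample size of 10 cannot be reproduced, because no alpha, power, effect size or SD is given. The documents also give no growth rate or session-to-session SD, so everything below is an illustration for percent words correct. It does not apply to TOMPD.

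**Assumed inputs.** Growth of 2 to 6 percentage points a year; session SD *s* of 3 to 6 points; baselines *g* = 1 to 3 weeks apart. **From the plan:** three baselines, end of treatment at 12 weeks, and a last visit six months later, taken as 12 + 26 = 38 weeks.

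**1. Growth.** Annual rate x weeks/52.

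- 12 weeks: 2 x 12/52 = 0.46; 6 x 12/52 = 1.38 points.
- 38 weeks: 2 x 38/52 = 1.46; 6 x 38/52 = 4.38 points.

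Counting from the middle baseline adds *g* weeks (13 to 15 and 39 to 41 weeks). This gives 0.5 to 1.7 and 1.5 to 4.7 points, which is little different.

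**2. Session noise for one boy.** One post-treatment value minus the mean of three baselines has SE = *s* x sqrt(1 + 1/3) = 1.155*s*.

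- SD treated as known: 1.96 x 1.155 = 2.26 SDs, a 95% half-width of 6.8 points (*s* = 3) to 13.6 points (*s* = 6).
- SD estimated from that boy's three baselines (2 df, t = 4.30): 4.30 x 1.155 = 4.97 SDs, or 14.9 to 29.8 points.

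This noise is a separate problem from growth, and a control would not remove it.

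**3. Could the baselines correct for growth?** A line through three baselines, projected to *w* weeks after the last one, has SE = sqrt(1/3 + (g + w)²/(2g²)) session SDs.

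| Spacing *g* | 12 weeks | 38 weeks |
|---|---|---|
| 1 week | 9.21 | 27.58 |
| 2 weeks | 4.98 | 14.15 |
| 3 weeks | 3.58 | 9.68 |

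Even in the best case the projection is uncertain by several session SDs, so it gives no usable correction.

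**4. Does having ten boys help?** It reduces noise but not a shared trend. With a known SD and the same growth in every boy, the mean change has half-width 6.79/sqrt(10) = 2.1 to 13.58/sqrt(10) = 4.3 points. Growth of 1.5 to 4.4 points at 38 weeks is of the same order and does not shrink with the number of boys.

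The documents give no basis for a figure for practice or concurrent therapy.

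**The case against.** The strongest reply is that the design is a reasoned choice. The protocol explains on ethical grounds why it has no control, cites a single-subject methods source, takes three baselines and three post-treatment assessments, replicates across ten boys, and provides for a statistician. On the illustrative figures, growth by 12 weeks is small, and most of one boy's uncertainty is noise that a control would leave in place. The protocol also says that improvement is not assured.

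Much of this stands. It shows that the study is worth doing and that growth alone is a weak explanation for a large early change. It does not supply a comparator: replication leaves shared growth and practice in place, and a later consultation cannot create a contrast that was never collected. The ethical argument does not touch the fix, which withholds nothing from any boy.

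A reader might go further and infer that no result could be informative. The documents do not support that. A large abrupt change at 12 weeks, repeated across boys, would be hard to put down to growth. Aim 2 also asks for a wider F2 difference "combined with improved perceptual identification of the low vowels (percent vowels correct) will implicate the effectiveness of intensive treatment on low vowels", a joint pattern that general practice is less likely to produce, though it too lacks a concurrent comparison.

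A reader might also take the high vowels as a ready-made untreated contrast. Approach says only that the low "vowels will supersede other vowel productions within each cycle of the treatment program". That sets a priority and does not say that the other vowels go unpractised. Such a contrast would not bear on TOMPD or percent words correct in any case.

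**Conclusion.** The concern holds for modest changes, and for changes seen only at six months, in TOMPD or percent words correct. These cannot be attributed to DS-DxTx, and the efficacy statements in Aim 1 and Potential Benefits exceed the design. This conclusion rests on the structure of the plan and needs none of the assumed figures.

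The size of any bias is unknown. Under the assumed growth it is about 0.5 to 1.4 points at 12 weeks and about three times that at 38 weeks, before any practice or therapy effect. The half-widths of 6.8 to 13.6 or about 15 to 30 points describe noise, and it would be a mistake to read them as bias from the missing control.

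Two further inferences should be resisted. The statement "The initial assessment also will include standardized testing using the Hodson Assessment of Phonological Processes-3 to customize treatment plan" might suggest that TOMPD has a single baseline score, but the text does not settle this and the point does not depend on it. The remark in Potential Benefits about surgical decisions is a general hope, with no decision rule attached.

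This should be fixed, but it is no reason to stop the study.

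**What to change.** 1. Add to Statistical Considerations: *There is no concurrent control. Changes in TOMPD and percent words correct will be reported as within-participant change. Modest changes, and changes seen only at six months, will not be attributed to DS-DxTx, because growth, task practice and concurrent therapy remain possible explanations. A large abrupt change at 12 weeks, repeated across boys, will be described as preliminary, uncontrolled evidence.* In Aim 1, replace the opening words with *Obtain preliminary, uncontrolled evidence on the efficacy of*. In Potential Benefits, say that the study *can give preliminary, uncontrolled evidence on* the strategy. Since the documents give no SD, the line between modest and large should be agreed with the statistician before results are seen.

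2. Add to Statistical Considerations: *Each boy's results will be shown by whether concurrent therapy targeted phonology, and by any change in therapy during follow-up.* The IEP, treatment targets and Parent Questionnaire already requested are the source.

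The cost is wording in three sections, one descriptive table and a more modest efficacy claim. No visit, assessment or treatment changes.

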#### Measures: Baseline, Primary and Secondary Outcome Measures

All assessments, treatments and post treatment assessment will be performed by a certified Speech-Language Pathologist with an assistant present.

- 1. Following consent, an initial assessment will be completed to obtain baseline and primary outcome measures as follows:
  - a. Current speech-language assessments (acoustic measures and language samples).
    - An audio recording of words/sentences of VTLab Speech Production Protocol (#2016-1025) and a language sample will be made using a Shure microphone and recording onto a Marantz MPD 660. This recording procedure is identical to IRB Protocol # 2016-1025. In brief, recording will entail: *a*) repetition of a list of words and sentences, and *b*) a spontaneous language sample of 1-3 minutes where participant may answer a question or tell a story.
      - a. Audio recordings will be used to assess treatment effectiveness via: *i*) acoustic analysis that entails making quantitative measurement of the speech signal including formant frequency measurements. *ii*) perceptual assessment by listeners to determine pre- post intelligibility score (% words correct, % consonants and vowels correct) comparison.
      - b. Language samples will be used to determine Mean Length of Utterance (MLU). When the sample is sufficiently lengthy, it will allow additional analyses that may include phonological calculation of the percent of consonants/vowels correct, token-to-token inconsistency measures, temporal measures, perceptual judgements of intelligibility by VTLab staff and/or naïve listeners, and consonant/vowel accuracy rating.

- ii. Standardized speech-language testing (to personalize treatment and assess its efficacy):
  - a. Hodson Assessment of Phonological Patterns, 3rd Edition [HAPP-3]
  - b. Language test for expressive/receptive measures (Peabody Picture Vocabulary Test- PPVT) Scoring of standardized tests will be completed in the manner described by their publisher or as additional documents listed in this IRB (e.g, Parent Questionnaire).
- b. Informal measures, questionnaire (speech-language history, current speech-language therapy/goals, family goals for speech intelligibility).
  - i. Oral Motor Exam/ Motor assessment.
  - ii. Intelligibility in Context Screening Form (ICS)
  - iii. Parent Questionnaire

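### Percent-correct intelligibility may be scored by laboratory staff alone, and the plan does not state masking to visit, random listening order or exclusion of treating staff

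*Combined protocol and SAP*

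**What the plan says.** Statistical Considerations defines the score: "intelligibility is scored as percent correct (words, consonants, vowels) based on the transcription of lab staff and/or naïve listeners". The Measures section describes the same comparison more loosely, as "perceptual assessment by listeners to determine pre- post intelligibility score (% words correct, % consonants and vowels correct) comparison". For language samples that are long enough, it again offers a choice between laboratory staff and naïve listeners for intelligibility judgements.

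The source material is recorded: "An audio recording of words/sentences of VTLab Speech Production Protocol (#2016-1025) and a language sample will be made", with the recording repeated at each post-treatment visit. Statistical Considerations also lists phonetic transcription by a trained speech-language pathologist, without saying whether this is the treating one.

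On roles, the Approach section says "Procedures for DS-DxTx will entail formal intervention by a certified Speech-Language Pathologist and one assistant", and the Measures section says "All assessments, treatments and post treatment assessment will be performed by a certified Speech-Language Pathologist with an assistant present".

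Two aims use the scores. Aim 1(b) is "Percent Words & Multisyllabic words Correct (with tabulation of percent consonants correct and percent vowels correct", and for Aim 2, "Perceptual measure will include percent accurate identification of the low vowels", before versus after treatment.

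**The concern.** Percent correct depends on what a listener believes he or she heard. The plan allows that listener to be a staff member who knows the boy, knows the visit, or has delivered the treatment. There is no concurrent control, and each of the ten boys is judged against his own baseline. Any tendency to hear later recordings more favourably therefore goes straight into the measured change.

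The study team has a stated expectation. The section on minimising risks anticipates that vowel treatment will prove effective, although the same sentence adds that this cannot be assured. At stake is whether a gain in percent correct can be read as a change in the boy's speech rather than in the scoring.

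**Working it through.** **Is there a safeguard elsewhere in the plan?** The relevant statements, side by side:

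- *Who scores.* Staff, naïve listeners or both (Statistical Considerations; Measures, for language samples). Naïve listeners are optional and the term is not defined.
- *Who treats and assesses.* The same professional role does both (Approach; Measures). No sentence separates therapist from scorer.
- *Coding.* The privacy sections and the section on minimising risks assign alpha-numeric codes to participants for confidentiality. The codes are not described as hiding the visit.
- *Listening order.* Not stated.
- *Outside sources.* The perceptual method is referred to a cited publication, and the recording task to a separate protocol. Neither can be checked here.

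So staff-only scoring with knowledge of the visit would comply with the text.

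**How scorer bias enters.** Let b_pre and b_post be the scorer's average error, in percentage points, on baseline and post-treatment files. For one boy:

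observed change = (post + b_post) − (pre + b_pre) = true change + (b_post − b_pre).

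If the lean is common to all boys, averaging over ten leaves b_post − b_pre untouched, and more boys would not remove it. Masking the visit and shuffling the files aims to make b_pre and b_post equal on average. The documents give no value for either term, so no bias size is computed.

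**Which outcomes are reached.**

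- *Aim 2, percent low vowels correct.* The Measures section ties percent vowels correct to the recordings, so this is exposed. Effectiveness is inferred only when a larger F2 difference accompanies better perceptual identification. Scorer bias can affect the perceptual half of that criterion, and also the other reading, in which unchanged vowel accuracy points to craniofacial cause.
- *Aim 1(b), percent words correct.* Exposed so far as it is scored from the recordings. The plan does not name the word list, and its description of the recordings does not mention multisyllabic words.
- *Aim 1(a), the HAPP-3 deviation score.* Outside this point.

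**Amount of material to mask.** Statistical Considerations gives three baseline measures and three post-treatment measures, but the plan does not say outright that a recording is made at every baseline.

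- Recording at all three baselines: 10 × (3 + 3) = 60 sets.
- Recording at one baseline only: 10 × (1 + 3) = 40 sets.

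**Delay if a boy's files are scored after his 6-month visit.**

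- End-of-treatment visit: 6 − 0 = 6 months.
- 1-month visit: 6 − 1 = 5 months.
- 6-month visit: 0.

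**The case against.** The strongest reply is that the quoted sentence summarises a method set out elsewhere. The cited publication or the separate recording protocol may already require masked, shuffled listening. That stands as a limit: the finding is about what this plan states, and the remedy may reduce to a citation. A reader might infer that scoring will be unmasked, or that the treating therapist will be the transcriber. The documents support neither; they only leave both open.

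Second, Aim 2 has a partial safeguard. Scorer bias alone cannot satisfy its effectiveness criterion, because the F2 difference is measured from the acoustic signal. The expectation is also less one-sided than it first appears, since unchanged vowel accuracy would be informative too. Both points stand and narrow the harm. They do not protect the perceptual half of the criterion, the unchanged-accuracy reading, or any part of Aim 1(b) scored from the recordings.

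Third, it is tempting to use listening position as a measure of size. If one listener heard a boy's six files in recorded order, post-treatment files would come on average (4 + 5 + 6)/3 − (1 + 2 + 3)/3 = 3 places later. No section gives a listening order, and a place in a queue is not a percentage-point bias, so this figure is not offered as a magnitude.

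Finally, this is a ten-boy study partly meant to supply preliminary data. That argues for proportion, but not for leaving an inexpensive gap open.

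**Conclusion.** The point holds in a limited form and should be fixed. The plan allows staff-only scoring of recording-based percent-correct and intelligibility measures, and states no masking to visit, no random order and no exclusion of treating staff. In an uncontrolled within-boy comparison this can bias the pre/post difference. The size of the bias is unknown and cannot be derived from the documents.

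The conclusion assumes that the recordings are the source of percent vowels correct, as the Measures section indicates, and of Aim 1(b) only to the extent that the sponsor confirms it.

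A reader might extend the point to the HAPP-3 score and call it live and unmasked. The plan does not support that: it says only "Scoring of standardized tests will be completed in the manner described by their publisher", and the absence of any mention of recording does not show how the test is scored.

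**What to change.** In Statistical Considerations, and in the language-sample wording of the Measures section, replace the open choice of scorer with a rule along these lines: the planned baseline, end-of-treatment, 1-month and 6-month recordings used for percent-correct and intelligibility scores are transcribed by naïve listeners, or by laboratory transcribers not involved in treatment; time-point labels are removed; files are shuffled in a separate random order for each listener; and transcription takes place after that boy's last visit.

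- Apply the same rule to the phonetic transcription listed in Statistical Considerations where it is done from recordings.
- State which word list yields Aim 1(b) and whether it is recorded.
- If the cited perceptual method or the separate recording protocol already requires masking and random order, say so and cite it.
- Add no statement that the HAPP-3 is scored live or unmasked.

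**Cost.** No new visit, participant or measure is needed. The work is relabelling and shuffling 40 to 60 recording sets. Final scores come about 6 months later for the end-of-treatment visit and 5 months later for the 1-month visit. The section on psychosocial risks lets families request results, so an early request would need a separate scoring that is kept out of the analysis. The plan does not confirm that transcribers outside treatment are available, but naïve listeners are already named.

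**What remains.** Masking may be imperfect if staff recognise a boy's voice, which favours listeners outside treatment. It does not address maturation, concurrent therapy, repeat testing or parent-reported forms.
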